	
 
• Patients must be willing and able to undergo lumbar punctures
 
• Patients who are OCB positive in their CSF (from previous diagnostic lumbar puncture)
 
 
Exclusion:
 
 
• Ineligible for oral cladribine under NHS England prescribing guidelines and those participating in MAGNIFY-MS study (cladribine tablets in active MS)
 
• Unsuitable to have a lumbar puncture (e.g. spinal deformity, tethered cord syndrome, or the use of aspirin or anticoagulants), and those unable to comply with study requirements, including frequency of visits and lumbar punctures
 
• Presence of comorbidities in which administration of cladribine is contraindicated
 
• Abnormal baseline investigations (WCC<3 x 10^9/l, neutrophil count < 1.5 x 10^9/l, platelet count < 100 x 10^9/l, haemoglobin < 110 g/l, LFT >/= 3x upper limit of normal site reference ranges, potassium < 2.8 mmol/l or > 5.5 mmol/l, sodium < 125 mmol/l, creatinine > 130 umol/l
 

Statistical methodology and analysis (if applicable)	
Changes in total immune cell counts will be analysed using descriptive statistics, including reduction relative to baseline and absolute reduction in numbers. Time to nadir and recovery will be done using best-fit modelling.
 
Total blood IgG and free kappa and lambda light chain levels will be normalised to albumin levels. McNemar's test will be used to compare differences in OCB status between baseline, year one or year two. The association between different biomarkers, clinical and imaging parameters will be analysed using multiple regression.

Study duration	96 weeks.

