### 6.5 Secondary endpoint

1. a. Relative change in CSF OCB pre- and post-cladribine (baseline vs 48w and 96w).
- b. Relative change in CSF cytokines and chemokines (baseline vs 48 w and 96w period), in particular CXCL-13 pre- and post-cladribine and urine neopterin levels.
- c. Relative change in CSF neurofilament light chain pre-and post-cladribine (baseline vs 48w and 96w).
- d. Relative change in blood immunoglobulin levels and T cell receptor levels (baseline vs 48 w and 96w period) pre-and post-cladribine and urine immunoglobulin levels.
2. Relative change in CSF soluble CD138 (plasma cell marker) pre- and post-cladribine (baseline vs. 48w and 96w).
3. Occurrence of CSF OCB positivity and relative change in CSF FLC post-cladribine *versus* historical data post-alemtuzumab (baseline vs. 48w and 96w).

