## 11. Statistical considerations

### 11.1 Sample size

This is an exploratory study and all analyses are descriptive. The primary endpoint of this study will be to look at the effect of oral cladribine on peripheral immunological markers over time. However, to explore the intrathecal effect of cladribine we will assess its impact on the disappearance of OCBs from the CSF. Based on published data none of the patients with MS will be expected to lose OCBs over 2 years of the study. With a power of 80%, and an alpha of 5%, we will only need 11 subjects to show a significant result if at least 50% of subjects on cladribine become OCB negative compared to a comparator group. Allowing for a 20% dropout rate we would only need to recruit 13 subjects.

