## 11.2 Method of analysis

Depletion and re-population kinetics of B and T cell subsets will be analysed using descriptive statistics. An interim analysis of the year 1 data is planned, and a further analysis of the whole data will be performed at the end of the study. These will be calculated as a reduction relative to baseline counts and the absolute reduction in numbers. Time to nadir and recovery will be done using best-fit modelling. Categorical data based on absolute cut-offs will be presented as proportions, e.g. for absolute lymphocyte counts this will use the WHO boundaries.

Total blood IgG and free kappa and lambda light chain levels will be normalised to albumin levels. McNemar's test will be used to compare differences in OCB status between baseline and year one CSF or year two CSF. Differences in CSF and blood biomarkers, clinical and imaging parameters between baseline and 48w and 96w will be analysed using multiple regression. A detailed SAP will be prepared and approved during the recruitment period well before data becomes available.

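### Does the plan need a stated rule for repeated measurements in its multiple regressions of biomarkers, clinical and imaging measures?

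*Combined protocol and SAP*

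**What the plan says.** Section 11.2 assigns methods by type of outcome.

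- Cell subsets, the primary endpoint: "Depletion and re-population kinetics of B and T cell subsets will be analysed using descriptive statistics". They are not part of this point.
- Oligoclonal band (OCB) status: McNemar's test, a paired method, "will be used to compare differences in OCB status between baseline and year one CSF or year two CSF".
- Other markers and measures: "Differences in CSF and blood biomarkers, clinical and imaging parameters between baseline and 48w and 96w will be analysed using multiple regression".

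The synopsis (section 4) words the regression differently: "The association between different biomarkers, clinical and imaging parameters will be analysed using multiple regression". It gives no visits and does not mention change.

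The endpoints behind these sentences are in sections 6.5 and 6.6. Section 6.5 defines most secondary endpoints as relative change from baseline to 48 and 96 weeks. Item 1b covers CSF cytokines and chemokines, "in particular CXCL-13 pre- and post-cladribine and urine neopterin levels". Section 6.6 item 2 asks for the correlation of immune cell profiles with EDSS, MSFC, MRI and MSIS-29 measures, each at baseline, 48 and 96 weeks, and of their changes.

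Two statements set the weight of all this. Section 11.1: "This is an exploratory study and all analyses are descriptive". Section 11.2: "A detailed SAP will be prepared and approved during the recruitment period well before data becomes available".

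**The concern.** Each patient can contribute three correlated records per marker. Multiple regression in its textbook form treats records as independent, and the plan gives no covariates, patient term or clustered standard error for it. OCB status gets an explicitly paired test and the continuous markers do not, which makes the silence more noticeable.

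The two sentences also serve different questions. Section 11.2 uses regression for change and the synopsis uses it for association, so 11.2 names no method for the correlations in section 6.6 item 2. That item lists all three visits on both sides, so pooling three records per patient would fit its wording. Urine neopterin is also not literally a CSF or blood biomarker.

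At stake are the intervals for the secondary biomarker changes (CXCL-13, neurofilament light chain, soluble CD138, immunoglobulins) and for the tertiary associations. Pooling would make the first too wide and the second too narrow.

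**Working it through.** **Inputs.** Three visits (section 6.5). For the number of patients, section 11.1 says: "Allowing for a 20% dropout rate we would only need to recruit 13 subjects". I use 13 with no loss, and 13 x 0.8 = 10.4, so 10, after dropout. The documents give no within-patient correlation, so rho = 0, 0.3, 0.5 and 0.7 are assumed, equal between all visits. The simulated figures use normal data on the log scale, 40,000 replicates and a two-sided 5% level.

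**The plan's own figure.** The only calculation in section 11.1 concerns OCB loss, 50% against 0%. With mean proportion 0.25:

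n = [1.96 x sqrt(2 x 0.25 x 0.75) + 0.8416 x sqrt(0.5 x 0.5)]^2 / 0.5^2 = 10.5, so 11 per group.

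This matches the stated 11. It does not depend on the regressions.

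**Change, as the text reads.** A change score per visit has one record per patient. Simulated type I error is 4.8 to 5.2%.

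**Change, if visits were pooled without a patient term.** The pooled standard error uses variance 2/n on 3n - 3 degrees of freedom. The paired one uses 2(1 - rho)/n on n - 1. The ratio of interval widths is therefore about (t with 3n - 3 df / t with n - 1 df) / sqrt(1 - rho). For n = 10 this is (2.052 / 2.262) / sqrt(1 - rho):

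| rho | 0 | 0.3 | 0.5 | 0.7 |
|---|---|---|---|---|
| Formula, n = 10 | 0.91 | 1.08 | 1.28 | 1.66 |
| Simulated, n = 10 | 0.92 | 1.10 | 1.30 | 1.68 |
| Simulated, n = 13 | 0.94 | 1.13 | 1.33 | 1.71 |

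The cost in power depends on an assumed effect. At n = 10 and rho 0.5, pooled against paired power is 12% and 29% for a change of 0.5 SD, 38% and 62% for 0.8 SD, and 80% and 92% for 1.2 SD.

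**Change, if the 48- and 96-week changes were stacked as independent.** They share a baseline, so under equal correlation they correlate 0.5 whatever rho is. The variance is understated by 1 + 0.5 = 1.5, and 1.96 / sqrt(1.5) = 1.60 gives a type I error of 11%. Simulation gives 10.9 to 11.5%.

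**Association, if three records per patient were pooled.** For unrelated markers with correlations rho1 and rho2, the variance is understated by about 1 + 2 x rho1 x rho2. Type I error is then the two-sided normal tail beyond 1.96 / sqrt(1 + 2 x rho1 x rho2):

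| rho1, rho2 | Factor | Formula | Simulated, n = 10 |
|---|---|---|---|
| 0, 0 | 1.00 | 5.0% | 5.0% |
| 0.3, 0.3 | 1.18 | 7.1% | 7.0% |
| 0.5, 0.5 | 1.50 | 11.0% | 10.6% |
| 0.7, 0.7 | 1.98 | 16.4% | 16.9% |
| 0.7, 0.3 | 1.42 | 10.0% | 9.7% |
| 0.7, 0 | 1.00 | 5.0% | 4.9% |

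The inflation needs both markers to persist within a patient. With one record per patient the simulated rate is 4.8 to 5.2%.

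**Which of these does the plan call for?** Section 6.5 sets the outcome as relative change from baseline at 48 and 96 weeks. Section 11.2 analyses differences between those same visits. Together they describe a within-patient change per visit, the valid case. Pooling visits and stacking changes appear nowhere. Section 6.6 item 2 can be read as pooled, but it also fits separate correlations at each visit, and it names changes as well. Both of those use one record per patient.

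**Urine neopterin.** The synopsis sentence covers different biomarkers without restriction to CSF and blood. Section 8 lists urine neopterin with the inflammatory markers, and section 11.1 makes every analysis descriptive. It is not left without a method.

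**The case for a change.** The strongest case for a change is that valid and invalid analyses both fit the wording, that an interval of the wrong width misleads even in a descriptive study, and that a few lines of text would close the gap. The SAP also has to build on a named method that differs between the synopsis and section 11.2.

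Part of this stands. The two sentences do serve different purposes, covariates are unstated, and the association analysis is open. The SAP author should settle all three.

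The rest does not carry far enough. The harmful analyses of change have to be read into the text, and the natural reading is the valid one. Writing a specific method into the plan would also be partly a matter of preference. A per-visit paired analysis needs no assumption about correlation between visits, but with equal correlation it gives up power to a model with patient terms (62% against 67% at n = 10, rho 0.5, 0.8 SD). With correlation that decays over time (adjacent-visit values of 0.3, 0.5 and 0.7), patient terms give type I errors of 6.8, 8.2 and 9.5% at n = 10. An unstructured repeated-measures model would also avoid the equal-correlation assumption. Limiting association models to values or changes at a single visit would bar relating an earlier immune profile to a later outcome, which section 6.6 item 2 allows.

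**Conclusion.** No change to the plan follows. The missing rule is modelling detail that a trial statistician supplies in the SAP, which section 11.2 commits to before data are available. For change, sections 6.5 and 11.2 already point to a within-patient difference at each visit, which is valid. For association there is a real ambiguity. Its worst size in the range examined is about 17% instead of 5%, if three records per patient are pooled and both markers have an assumed within-patient correlation of 0.7. It vanishes if either marker does not persist, or if each patient contributes one record. In writing the SAP, the analyst would be expected to reconcile the two sentences and keep each patient as the unit of analysis.

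The conclusion rests on assumed correlations of 0 to 0.7, on 10 to 13 patients, and on the SAP being written as promised. The primary endpoint is analysed descriptively. Neither the sample size, which concerns OCB loss, nor alpha depends on these regressions.

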## 12. Ethics

The Principal Investigator will ensure that the study is carried out in accordance with the ethical principles in the Research Governance Framework for Health and Social Care, Second Edition, 2005 and its subsequent amendments as applicable and applicable legal and regulatory requirements. A favourable opinion will be sought from NHS REC.

## 13. Public Involvement

The therapeutic strategy and concept employed in this trial have been discussed with service users and pwMS during Patient Engagement and focus group events. Results of the study will be shared within these events and also on the MS research blogspot: <http://multiple-sclerosis-research.blogspot.com/>.

## 14. Data handling and record keeping

### 14.1 Data management

Study data will be captured in source documents such as the hospital medical notes, laboratory reports, ECG print-outs and study-specific source document worksheets. Data will be entered into the case report form (CRF) by delegated members of the study team. All data generated by the study will be stored securely with a full audit trail.

## 14.2 Source data

Data will be recorded from a variety of sources including participant-reported information, physical examination findings, and print-outs from equipment, recording results from electronic displays, laboratory reports and validated questionnaires. All efforts will be made to maximise completeness of data e.g. telephoning subjects. All interactions with participants will be documented (e.g. telephone conversations). Questionnaires will be completed by participants and that every questionnaire should be data and signed by the person completing it. The CI/delegate will keep records of all participants (sufficient information to link records e.g., CRFs, hospital records and samples), all original signed informed consent forms and copies of the CRF pages. All data generated by the study will be stored securely with a full audit trail.

## 14.3 Confidentiality

Information related to participants should be kept confidential and managed in accordance with the Data Protection Act, NHS Caldecott Principles, The Research Governance Framework for Health and Social Care, and the conditions of Research Ethics Committee Approval.

## 14.4 Record Retention and Archiving

When the research trial is complete, it is a requirement of the Research Governance Framework and Trust Policy that the records are kept for a further 20 years. For trials involving BH Trust patients, undertaken by Trust staff, or sponsored by BH or QMUL, the approved repository for long-term storage of local records is the Trust Corporate Records Centre. All research documentation will be archived in physical form.

# 15. Laboratories

## 15.1 Central and local laboratories

Specimen collection and processing: standard operating procedures will be in place outlining CSF, blood and urine and collection, transport, processing and storage either to the relevant Barts Health NHS Trust laboratory for routine specimens or to the Blizzard Institute research laboratories for research samples.

## 15.2 Sample collection and preparation

Specimen collection, handling and processing will be performed in accordance with written SOPs. Because the adequacy of the specimen will affect the accuracy and usefulness of the biomarker results, all CSF will be processed within an hour of collection, whilst the quality of the blood specimen will be assessed for general interferences, such as haemolysis and lipemia by RLH Pathology Labs. Samples will have a unique identifier with participant details anonymized and stored at -80C until required for analysis.

## 15.3 Laboratory procedures

Four (serum, whole blood and cells) additional samples of venous blood will be taken during the venepuncture to obtain their routine clinical blood tests. The whole blood will be stored for future ImmunoSEQ analysis. The CSF collection and urine collection would also be an additional tests. Because the adequacy of the specimen will affect the accuracy and usefulness of the biomarker results, all CSF will be processed within an hour of collection, whilst the quality of the blood specimen will be assessed for general interferences, such as haemolysis and lipemia by Barts Health NHS Trust Pathology Labs. Samples will have a unique identifier with participant details anonymized.

PBMC Preparation: Peripheral blood mononuclear cells (PBMCs) will be obtained from venous blood by density gradient centrifugation using Ficoll (Invitrogen). Briefly the blood will be diluted 1:1 in PBS (without Ca2+, Mg2+) and 25ml loaded on Ficoll in a 1:1 ratio. Tubes will then be centrifuged for 30min at 1500rpm at 20°C. The buffy coat will be collected in a 50ml tube and washed twice in PBS. Finally the pellet will be resuspended in 1ml PBS and cells counted with haemocytometer.

Extracellular Staining: Cells will be washed twice with 500ul of FACS buffer (2% FBS, 2mM EDTA in PBS). Cells will then be blocked for 20 minutes in the dark with 100ul of blocking solution (FACS buffer). Cells will then be labelled with antibodies of interest (anti-live, anti-CD3, anti-CD10, anti-CD19, anti-CD25, anti-CD27, anti-CD38, anti-IgD; BD). They will be left for 30 minutes on ice before being washed twice with FACS, then centrifuged for 5 minutes at 1300 and 4°C. The pellet will be resuspended in 200ul of FACS buffer. They will then be analysed.

## 15.4 Sample storage and transfer

The routine blood tests will be sent to the NHS pathology laboratory at the Royal London Hospital. The additional sample will be transferred by hand to the laboratory at the Blizard Institute. Aside from the PBMCs (see above), samples will be stored at -80C awaiting analysis.

## 16. Interventions and tools

### 16.1 Medicinal product

Participants will receive oral cladribine based on licensed indication for cladribine (Mavenclad, Merck Serono) in RRMS (NICE TA493) under the NHS. In the summary of product characteristics the recommended cumulative dose is 3.5 mg/kg body weight over 2 years, taken as 1 treatment course of 1.75 mg/kg per year. Each treatment course consists of 2 treatment weeks, 1 at the beginning of the first month and 1 at the beginning of the second month of the respective treatment year. Each treatment week consists of 4 or 5 days on which a patient takes 10 mg or 20 mg (1 or 2 tablets) as a single daily dose, depending on body weight. Following completion of the 2 treatment courses, no further cladribine treatment is required in years 3 and 4. Cladribine will be stored and dispensed by the Barts Health NHS Trust pharmacy.

## 17. Safety reporting

Adverse Events (AEs) and Adverse Reactions (ARs) will be recorded. Serious Adverse Events (SAEs) and Serious Adverse Reactions (SARs) will be reported to the CI as medical assessor for the sponsor and coordinating team. All unexpected SARs (SUSARs) will be reported to the JRMO and REC.

### 17.1 Adverse Events (AEs)

An AE is any untoward medical occurrence in a participant to whom an intervention has been administered, including occurrences which are not necessarily caused by or related to that intervention. An AE can therefore be any unfavourable or unintended sign (including an abnormal laboratory finding), symptom or disease temporally associated with study activities.

### 17.2 Adverse Reaction (ARs)

An AR is any untoward and unintended response in a participant to an intervention. All adverse events judged by either the reporting investigator or the sponsor as having a reasonable causal relationship to the intervention qualify as adverse reactions. The expression 'reasonable causal relationship' means in general that there is evidence or an argument to suggest a causal relationship.

### 17.3 Notification and reporting of Adverse Events and Reactions

If the AE is not defined as serious, the AE will be recorded in the study documents and the participant followed up by the research team. The AE will be documented in the participants' source documents, the Case Report Form (CRF), and, where appropriate, medical records.

### 17.4 Serious Adverse Events (SAEs) or reactions

A serious adverse event (SAE) is defined as an untoward occurrence that:

- Results in death,
- Is life-threatening,
- Requires hospitalisation or prolongation of existing hospitalisation,
- Results in persistent or significant disability or incapacity,
- Consists of a congenital anomaly or birth defect, or
- Is otherwise considered medically significant by the investigator.

SARs will be reported to the REC where in the opinion of the Chief Investigator the event was serious and:

- Related (it may have resulted from administration of any of the research interventions), and
- Unexpected (the type of event is not listed in the protocol or other Reference Safety Information as an expected occurrence).

### 17.5 Notification and reporting of Serious Adverse Events

Serious Adverse Events (SAEs) that are considered to be 'related' and 'unexpected' will be reported to the sponsor and the funder of the studied medicinal product within 24 hours of learning of the event, and to the REC within 15 days in line with the required timeframe.

### 17.6 Urgent Safety Measures

The CI will take urgent safety measures if necessary to ensure the safety and protection of the clinical study participant from immediate hazards to their health and safety. The measures will be taken immediately. The approval of the REC prior to implementing urgent safety measures is not required. However the CI will inform the sponsor and Research Ethics Committee (via telephone) of this event immediately.

The CI will inform the REC in writing within 3 days, in the form of a substantial amendment. The sponsor (Joint Research Management Office (JRMO)) will be sent a copy of the correspondence with regards to this matter.

## 17.7 Annual Safety Reporting

The CI will send the Annual Progress Report to the REC using the HRA template (the anniversary date is the date on the REC “favourable opinion” letter) and to the sponsor.

## 17.8 Overview of the Safety Reporting responsibilities

The CI is the medical assessor on behalf on the sponsor and will review all events reported. The CI will ensure that safety monitoring and reporting is conducted in accordance with the sponsor’s requirements.

## 18. Monitoring and auditing

The sponsor or delegate retains the right to audit any study, study site, or central facility. Any part of the study may be audited by the funders, where applicable.

Study will be monitored as per sponsors SOPs and internal audits may be conducted by the sponsor. Monitoring will include source data verification.

## 19. Trial committees

There will be regular meetings between the PI, and research fellow as part of study management. The safety committee will comprise of the PI and co-investigators (Barts Health NHS Trust neurologists) who will address any safety issues that may arise in the study.

## 20. Finance and funding

The study is funded by Merck Serono Ltd. ([name]).

## 21. Indemnity

NHS indemnity scheme will apply. It provides cover for the design, management, and conduct of the study.

## 22. Dissemination of research findings

Patients will be asked at the time of consent whether they would like to be informed of the study outcome. If they request to be informed, they will be contacted by post with a lay summary of the trial findings.

Depending on the study outcome, it may be published in a peer-reviewed scientific journal, and the conclusions disseminated through poster presentation at an international conference.

